In the Phase 2 FC study, Lin-MD-67, children (2- to 5-year-olds), were administered linaclotide doses of 18, 36, and 72 µg for 4 weeks. Those doses correspond to 1.8, 3.6, and 7.2 µg/kg in a 10 kg (22 pound) subject (minimum weight of a 2-year-old), respectively. Overall linaclotide was well tolerated across all doses evaluated in LIN-MD-67, the safety profile being consistent with that of the prior FC study LIN-MD-62 in 6 to 17 year-olds and prior studies in adults with CIC. There were no deaths, SAEs, AESIs (i.e., significant volume depletion and/or significant electrolyte abnormalities and/or ECG abnormalities that were considered by the investigator or sponsor to be related to diarrhea), or AEs leading to study drug discontinuation for LIN-MD-67 with all TEAEs experienced by subjects being mild or moderate in severity.

Additionally, in the GC-C ontogeny study MCP-103-311, GC-C mRNA expression in the small bowel was shown to be flat with no age-dependent trend in patients 6 months to < 18 years of age.⁶ The doses of 9, 18, and 36 µg QD being employed in Study M21-862 correspond to 1.8, 3.6 and 7.2 µg/kg in a 5 kg (11 pound) subject (minimum weight of a 6 month old), respectively and are therefore equivalent to the doses tested and safe in 2- to 5- year-old subjects on µg/kg basis and are expected to have an acceptable safety profile. Dose escalation between cohorts will be assessed based on the review of all available safety/tolerability data by an internal Dose Escalation Committee. Regarding risks, patients are closely monitored for AEs including diarrhea and well-defined AESIs. Safety measures are in place including stopping criteria, a safety monitoring plan, and an independent DSMB.

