3.11 Vital Signs (including weight) and Postural Vital Signs

Vital signs and postural vital signs will be obtained and documented as noted in Section 2.1. Vital signs will be assessed as follows:

Vital signs include weight, temperature, and respiratory rate; postural vital signs (supine and standing whenever possible according to subject's age) include pulse rate and systolic and diastolic blood pressure. If possible, temperature should be obtained using the same method throughout the course of the study. Blood pressure and pulse measurements should be preceded by at least 5 minutes of rest for the subject in a quiet setting.

At all visits, postural vital signs must be obtained after subjects have been in a supine position for at least 2 to 3 minutes, followed by a stationary position for at least 1 minute. Measurements should be assessed consistently throughout the study. Vital signs measurements determined prior to dosing on Day 1 will serve as baseline.

Measurements should be assessed consistently throughout the study. Vital signs measurements determined prior to dosing on Day 1 will serve as baseline.

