2.2 Study Design Overview

M21-862 is a phase 2 study to assess the safety of linaclotide (Part 1) and to evaluate the safety and efficacy of linaclotide in pediatric subjects (Part 2) (6 months to less than 2 years of age). The schematic of the study is shown in [Figure 1](#) and [Figure 2](#). Further details regarding study procedures are in the Protocol Operations Manual.

This study consists of 2 Parts that include 4 cohorts in total. Part 1 has three open-label cohorts and Part 2 has a double-blind cohort. Part 1 cohorts will be open label and enrolled sequentially with linaclotide in ascending doses. A linaclotide dose will be chosen for Part 2 based on the overall benefit-risk profile of the open-label cohorts in Part 1. Part 2 will include a double-blind cohort to assess the efficacy of linaclotide vs. placebo. All cohorts will have a study intervention period of 4 weeks.

[figure not shown]
The schematics of the study and the study visit for Parts 1 and 2 are shown in [Figure 1](#) and [Figure 2](#).

Figure 1. Study Schematic

TBD = to be determined in Part 1.

Figure 2. Study Visit Schematic Parts 1 and 2

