10.0 Safety Analyses

10.1 General Considerations

Safety analyses will be performed on the safety analysis population in the 4-week OL period (Part 1) and the 4-week DB period (Part 2). Safety summary will be presented for each cohort in Part 1 and by treatment group in Part 2. Additionally, if any cohort has a the same linaclotide dose as the other cohorts, pooled summaries will also be provided.

The Baseline for safety analysis is defined as the last available measurement before the first study drug administration for each cohort, except the following:

- For subjects enrolled in 2 cohorts (Cohort 1 and Cohort 2; or Cohort 2 and Cohort 3), if subjects enroll into the next cohort within 28 days of last dose of the previous cohort, the baseline of the first cohort will be used the baseline for the second cohort.
- For subjects enrolled in all 3 cohorts (Cohort 1, Cohort 2, and Cohort 3), if subjects enroll into the second cohort and the third cohort within 28 days of last dose of the previous cohort, the baseline of Cohort 1 will be used the baseline for the second and third cohort.

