Urinalyses Variables	Units	Definition of Potentially Clinically Important	
		Very Low	Very High
pH	—	< 0.9 × LLN	> 1.1 × ULN
Specific gravity	—	—	> 1.1 × ULN

LLN = lower limit of normal value provided by the laboratory; SI = Le Système International d'Unités (International System of Units); ULN = upper limit of normal value provided by the laboratory

Table C-4. Criteria for Potentially Clinically Important Vital Sign Values

Urinalyses Variables	Flag	Observed Value	Criteria ^a
Systolic Blood Pressure, mmHg - Postural Vital Signs (Supine and Standing)		Decrease in systolic blood pressure of 20 mmHg or more from supine to standing [*Change from supine SBP <= -20]	Decrease in systolic blood pressure from supine to standing at observed time point is at least 10 mmHg greater than the decrease in systolic blood pressure from supine to standing at baseline [Postbaseline change from supine SBP – baseline change from supine SBP <= -10]
Diastolic Blood Pressure, mmHg Postural Vital Signs (Supine and Standing)		Decrease in diastolic blood pressure of 10 mmHg or more from supine to standing [Change from supine DBP <= -10]	Decrease in diastolic blood pressure from supine to standing at observed time point is at least 10 mmHg greater than the decrease in diastolic blood pressure from supine to standing at baseline [Postbaseline change from supine DBP – baseline change from supine DBP <= -10]
Pulse Rate, bpm - Postural Vital Signs (Supine and Standing)		Increase in heart rate of 20 beats per minute or more from supine to standing [Change from supine pulse rate >= 20]	Increase in heart rate from supine to standing at observed time point is at least 10 beats per minute greater than the increase in heart rate from supine to standing at baseline [Postbaseline change from supine pulse rate – baseline change from supine pulse rate >= 10]
Systolic Blood Pressure, mm Hg (Supine)	High	Age 6-24 months (inclusive): ≥ 125	Increase of ≥ 20
	Low	Age 6-24 months (inclusive): ≤ 70	Decrease of ≥ 20
Diastolic Blood Pressure, mm Hg (Supine)	High	Age 6-24 months (inclusive): ≥ 85	Increase of ≥ 15
	Low	Age 6-24 months (inclusive): ≤ 35	Decrease of ≥ 15
Pulse Rate, bpm (Supine)	High	Age 6-24 months, boy (inclusive): ≥ 165 Age 6-24 months, girl (inclusive): ≥ 188	Increase of ≥ 15
	Low	Age 6-24 months, boy (inclusive): ≤ 87 Age 6-24 months, girl (inclusive): ≤ 85	Decrease of ≥ 15
Weight, kg	High	—	Increase of $\geq 10\%$
	Low	—	Decrease of $\geq 5\%$

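### SAP 10.1 carries the first cohort's baseline forward for weight too, so weight change reported under a later dose includes earlier growth and can mask loss on that dose

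*SAP*

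**What the plan says.** SAP 10.1 starts from a baseline specific to each cohort, "defined as the last available measurement before the first study drug administration for each cohort, except the following". The exceptions concern Part 1 children who escalate.

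- For a child in two cohorts who starts the second within 28 days of the last dose in the first, "the baseline of the first cohort will be used the baseline for the second cohort". A child who enters at Cohort 2 and moves to Cohort 3 therefore keeps the Cohort 2 baseline.
- For a child in all three, "if subjects enroll into the second cohort and the third cohort within 28 days of last dose of the previous cohort", then "the baseline of Cohort 1 will be used the baseline for the second and third cohort".

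No variable is exempt. SAP 10.4 counts body weight among the vital signs and presents its change from baseline at each time point. Table C-4 in SAP Appendix C makes a weight potentially clinically important (PCI) on percentage change alone: a rise of at least 10% or a fall of at least 5%, with no adjustment for age or growth. SAP 10.4 ties the PCI table to the double-blind period, although the same paragraph speaks of the corresponding cohort and SAP 10.1 promises safety summaries for each Part 1 cohort.

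Section 3.11 of the protocol's Operations Manual says: "Vital signs measurements determined prior to dosing on Day 1 will serve as baseline". It does not mention children who escalate.

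**The concern.** Carrying an untreated baseline forward is reasonable for a quantity that would stay roughly level without treatment. Weight at 6 to 24 months does not stay level, and Protocol 7.5 itself describes height and weight as growth parameters. For an escalating child, the change tabulated under Cohort 2 or 3 is growth since the first cohort plus whatever happened on the current dose.

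This sits badly with SAP 10.2.1, which closes each cohort's adverse-event window no later than the first dose in the next cohort. Adverse events are assigned to the dose being taken, while weight change accumulates over two or three doses and is reported under the last.

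Weight matters here because it is an objective measure taken at every visit, and dehydration due to diarrhoea that leads to hospitalisation is an adverse event of special interest (Protocol 6.1). What is at stake is the by-cohort weight summary at the two higher doses.

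**Working it through.** The plan states neither a growth rate nor the time from baseline, so there is no figure of its own to reproduce.

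**Inputs.** Treatment length is 4 weeks in every cohort (SAP 2.2: "All cohorts will have a study intervention period of 4 weeks"). The gap from last dose to the next cohort is 0 to 28 days for the carry-forward rule to apply (SAP 10.1). The weight limits are +10% and -5% (Table C-4). Growth is assumed to be 1% to 5% per month.

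**Step 1: time from the carried-forward baseline.**

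| Cohort, in the child's own sequence | Starts, weeks after baseline | Treatment ends |
|---|---|---|
| Second, no gap | 4 | 4 + 4 = 8 |
| Second, 28-day gap | 4 + 4 = 8 | 12 |
| Third, no gaps | 8 | 12 |
| Third, two 28-day gaps | 4 + 4 + 4 + 4 = 16 | 20 |

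The postintervention visit adds one week; visit windows are ignored.

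**Step 2: growth before the cohort starts.** With r the monthly rate and w the weeks elapsed, g = (1 + r)^(7w/30.44) - 1.

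**Step 3: loss needed to show a 5% decrease.** Measured from the weight on Day 1 of the current cohort, this is L = 1 - 0.95/(1 + g). Whenever g is above zero, L is above 5%.

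**Step 4: how a true 5% loss from that Day 1 weight would appear.** S = 0.95(1 + g) - 1.

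| Cohort starts after | Monthly growth | g | L | S |
|---|---|---|---|---|
| 4 weeks | 1% | 0.9% | 5.9% | -4.1% |
| 4 weeks | 5% | 4.6% | 9.2% | -0.6% |
| 8 weeks | 1% | 1.8% | 6.7% | -3.2% |
| 8 weeks | 5% | 9.4% | 13.2% | +3.9% |
| 16 weeks | 1% | 3.7% | 8.4% | -1.5% |
| 16 weeks | 5% | 19.7% | 20.6% | +13.7% |

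For example, at 16 weeks and 5%: 1.05^(112/30.44) = 1.197, L = 1 - 0.95/1.197 = 20.6%, and S = 0.95 × 1.197 - 1 = +13.7%. In no row does a true 5% loss reach the 5% limit.

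**Step 5: when growth alone reaches +10%.** The monthly rate needed is 1.10^(30.44/(7w)) - 1: 5.3% over 8 weeks, 3.5% over 12 weeks and 2.1% over 20 weeks. The only age-specific weights in the documents are the minimum weights of 5 kg at 6 months and 10 kg at 2 years in Protocol 4.2. Joined geometrically they give (10/5)^(1/18) - 1 = 3.9% per month, above the 12- and 20-week thresholds. They are minimum weights used to express dose per kilogram, not a growth curve, so this is only an illustration.

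**Step 6: with each cohort's own Day 1 weight.** The span is 4 weeks in every cohort. Expected growth over it is 0.9% to 4.6%, a +10% change from growth alone would need 10.9% per month, and a true 5% loss from Day 1 shows as 5%.

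**The case against.** The case against giving this much weight is substantial, and several parts of it stand.

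- **High-weight flags.** A reader might infer that the rule will label normal growth as potentially clinically important. The documents do not establish that. As worded, SAP 10.4 produces the PCI table for the double-blind period. Only Part 2 is double-blind, and it recruits new children, so carry-forward never applies there. False flags need both a PCI table run for Part 1 and growth above the rates in Step 5.
- **Dose decisions.** A reader might infer that escalation or dose choice is compromised. Protocol 4.1 names treatment-related events of special interest, SBM frequency and stool form as selection criteria, not weight change. The escalation committee works under a separate charter.
- **Contradiction with the Operations Manual.** Section 3.11 does not say which cohort's Day 1 applies to an escalating child, and Day 1 of the first cohort is also pre-dose. The text is unclear rather than contradictory.
- **Other vital signs.** The growth argument covers weight. For pulse and blood pressure an untreated baseline is as defensible as it is for laboratory values and ECG.
- **Few children.** Only children who have not improved and who tolerate the drug may escalate, and the committee must first review a cohort with at least five completers. Some gaps will exceed 28 days, in which case the child gets a new baseline.
- **Other routes to the signal.** Subject listings are promised (Protocol 7.5), observed weights are summarised, and adverse events are assigned by cohort.

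The last point softens the consequence but does not correct the tabulated change, which remains wrong for its purpose. With six children per cohort, one affected child can be about a sixth of a summary.

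**Conclusion.** The point holds for body weight. The change-from-baseline summaries for Cohorts 2 and 3 will mix growth from earlier cohorts with change on the current dose for any child who escalated within 28 days. The direction does not depend on the growth rate: any positive growth before the cohort starts makes loss on that dose look smaller. The size does depend on it. At 1% to 5% per month, the loss needed to show a 5% decrease is 5.9% to 13.2% in a second cohort and 6.7% to 20.6% in a third, across the permitted gaps.

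The 12-to-20-week span belongs only to a third cohort. A second cohort, including Cohort 3 for a child who entered at Cohort 2, spans 8 to 12 weeks. This is a reporting defect worth correcting in a small descriptive study; it is not evidence that a safety decision would go wrong.

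**What to change.** Add to SAP 10.1:

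*For body weight, change from baseline and PCI status in each cohort use the pre-dose Day 1 (Visit 3) weight of that cohort, irrespective of the gap since the previous cohort; change from the first cohort's baseline is also shown for subjects in more than one cohort.*

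Keep the carry-forward rule for laboratory values, ECG, pulse and blood pressure. State in SAP 10.4 whether the PCI tables cover the Part 1 cohorts. Keeping the first-cohort comparison preserves sight of cumulative loss across doses.

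The cost is one SAP sentence, one clarification and an extra column for a few children. The activity schedule already places weight at Visit 3, where study drug is dispensed and first given, so no new measurement or protocol amendment is needed. This assumes that an escalating child has a Visit 3 in each cohort; the documents do not say so outright, and the SAP author should confirm it.

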10.2 Adverse Events

Adverse events (AEs) will be summarized and presented using primary MedDRA System Organ Classes (SOCs) and preferred terms (PTs) according to the version of the MedDRA coding dictionary used for the study at the time of database lock. The actual version of the MedDRA coding dictionary used will be noted in the AE tables and in the clinical study report. Specific AEs will be counted once for each subject for calculating percentages, unless stated otherwise. In addition, if the AE event occurs multiple times within a subject, the highest severity and level of relationship to investigational product will be reported for the corresponding cohort.

10.2.1 Treatment-Emergent Adverse Events

The Treatment-Emergent Adverse Events (TEAEs) for the SA population are defined as follows.

Part 1

Cohort 1: TEAEs are defined as events that begin either on or after the first dose of OL linaclotide study drug in Cohort 1 and whichever are earlier of the following:

- the first dose of study drug in Cohort 2
- 30 days after the last dose administration of the study drug in Cohort 1

Cohort 2: TEAEs are defined as events that begin either on or after the first dose of the study drug in Cohort 2 and whichever are earlier of the following:

- the first dose of study drug in Cohort 3
- 30 days after the last dose administration of the study drug in Cohort 2

Cohort 3: TEAEs for Cohort 3 are defined as events that begin either on or after the first dose of the study drug in Cohort 3 and 30 days after the last dose administration of the study drug in Cohort 3.

Part 2

TEAEs for Part 2 are defined as events that begin either on or after the first dose of study drug in Part 2 and within 30 days after the last dose administration of the study drug.

Events where the onset date is the same as the study drug start date are assumed to be treatment-emergent. All treatment-emergent AEs will be summarized overall, as well as by primary MedDRA SOC and Preferred Term. The SOCs will be presented in alphabetical order, and the PTs will be presented in alphabetical order within each SOC.

If an incomplete onset date was collected for an AE, the event will be assumed to be treatment-emergent unless there is other evidence that confirms that the event was not treatment-emergent (e.g., the event end date was prior to the study drug start date).

The number and percentage of subjects experiencing TEAEs will be summarized by cohort in Part 1 and by treatment group for Part 2.

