Persistent or Significant Disability/Incapacity	An event that results in a condition that substantially interferes with the activities of daily living of a study subject. Disability is not intended to include experiences of relatively minor medical significance such as headache, nausea, vomiting, diarrhea, influenza, and accidental trauma (e.g., sprained ankle).

**Important Medical Event
Requiring Medical or Surgical
Intervention to Prevent
Serious Outcome**

An important medical event that may not be immediately life-threatening or result in death or hospitalization, but based on medical judgment may jeopardize the subject and may require medical or surgical intervention to prevent any of the outcomes listed above (i.e., death of subject, life threatening, hospitalization, prolongation of hospitalization, congenital anomaly, or persistent or significant disability/incapacity). Additionally, any elective or spontaneous abortion or stillbirth is considered an important medical event along with any suspected transmission of an infectious agent via a medicinal product if no other serious criterion is applicable. Examples of such events include allergic bronchospasm requiring intensive treatment in an emergency room or at home, blood dyscrasias or convulsions that do not result in inpatient hospitalization, or the development of drug dependency or drug abuse.

All adverse events reported from the time of study drug administration up to 30 days, after discontinuation of study drug administration will be collected, whether solicited or spontaneously reported by the subject. After 30 days, following the last dose of study drug or completion of study treatment only spontaneously reported SAEs will be collected (nonserious AEs will not be collected). In addition, study procedure-related serious and nonserious adverse events will be collected from the time the subject signs the study-specific informed consent.

The following definitions will be used for Serious Adverse Reactions (SAR) and Suspected Unexpected Serious Adverse Reaction (SUSAR):

SAR	Defined as all noxious and unintended responses to an IMP related to any dose administered that result in an SAE as defined above.

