5.2 Treatment After End of Study

For subjects enrolled in Part 1 (Cohorts 1-3) or randomized to Part 2, subjects will continue study treatment throughout the study for a period of up to 28 days per cohort or until premature

discontinuation of study drug. At the subject's last study visit, the investigator will discuss the appropriate subsequent treatment with the subject. If symptoms improve at the current dose level, the subject will be given the option to participate in a long-term safety extension study, once the study is active and accepting subjects.

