Laboratory abnormalities will be evaluated based on Potentially Clinically Important (PCI) criteria ([Appendix C](#)). For each laboratory PCI criterion, the number and percentage of subjects who have a laboratory value meeting the criteria will be summarized by treatment group. Listings will be provided to summarize subject-level laboratory data for subjects meeting PCI criteria. The percentages will be calculated relative to the number of subjects with available non-PCI baseline values and at least 1 postbaseline assessment for the assessment period. The numerator will be the total number of subjects with available non-PCI baseline values and at least 1 PCI postbaseline assessment for the assessment Period. A supportive tabular display of subject with PCI postbaseline values will be provided.

Potential Hy's Law

Potential Hy's Law criteria within a 24-hour window is defined by a postbaseline elevation of ALT or AST $\geq 3 \times$ ULN, along with TBL $\geq 2 \times$ ULN and a non-elevated ALP $< 2 \times$ ULN, all based on blood draws collected within a 24-hour period.

Subjects who meet the potential Hy's Law criteria from the first dose of study drug to within 30 days after the last dose of treatment will be summarized. Supportive tabular displays will also be provided.

Assessment of Liver Enzyme and Bilirubin Elevations

The liver-specific laboratory tests include the serum glutamic pyruvic transaminase (SGPT/ALT), serum glutamic-oxaloacetic transaminase (SGOT/AST), alkaline phosphatase (ALP), and total bilirubin (TBL). The frequencies and percentages of subjects with post baseline liver specific function test values that meet the following criteria of potential clinical interest will be summarized by treatment group:

- ALT $\geq 3 \times$ ULN
- ALT $\geq 5 \times$ ULN
- ALT $\geq 10 \times$ ULN
- ALT $\geq 20 \times$ ULN
- AST $\geq 3 \times$ ULN
- AST $\geq 5 \times$ ULN
- AST $\geq 10 \times$ ULN
- AST $\geq 20 \times$ ULN
- TBL $\geq 2 \times$ ULN
- ALP $\geq 1.5 \times$ ULN
- ALT or AST $\geq 3 \times$ ULN
- ALT and/or AST $\geq 3 \times$ ULN and TBL $\geq 1.5 \times$ ULN
- ALT and/or AST $\geq 3 \times$ ULN and TBL $\geq 2 \times$ ULN
- ALT or AST $\geq 5 \times$ ULN for more than 2 weeks

- ALT or AST $\geq 8 \times$ ULN

where ULN is the upper normal limit. The maximum ratio relative to the ULN will be used to determine if subjects meet any of the criteria listed above.

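### The TEAE windows do not close at the first dose in the long-term extension, so AEs starting on extension treatment could be counted against the Part 2 arm or Part 1 cohort just left

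*SAP*

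**What the plan says.** SAP 10.2.1 defines the TEAE window separately for each cohort.

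- Cohort 1 ends at the earlier of "the first dose of study drug in Cohort 2" or 30 days after its own last dose. Cohort 2 ends at the earlier of "the first dose of study drug in Cohort 3" or 30 days.
- Cohort 3 has no such cut: its window lies between the start of "the study drug in Cohort 3 and 30 days after the last dose administration of the study drug in Cohort 3", with no earlier end.
- Part 2 takes events that begin on or after first dose "in Part 2 and within 30 days after the last dose administration of the study drug".

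Operations Manual 5.2 opens with "For subjects enrolled in Part 1 (Cohorts 1-3) or randomized to Part 2" and goes on: "If symptoms improve at the current dose level, the subject will be given the option to participate in a long-term safety extension study". The offer depends on the extension being active and accepting subjects. Protocol 4.1 and SAP 2.3 also mention the extension for children who have improved at their current dose.

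On collection, Protocol 6.1 states: "All adverse events reported from the time of study drug administration up to 30 days, after discontinuation of study drug administration will be collected". Operations Manual 4.1 repeats the 30-day period. The potential Hy's law summary in SAP 10.3 uses the same tail: cases from first dose to "within 30 days after the last dose of treatment will be summarized".

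**The concern.** The Cohort 1 and 2 rule reflects a sound principle: attribution to one exposure stops when the next begins. The SAP applies it between cohorts but not at extension entry.

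Even for Cohorts 1 and 2 the existing cut misses the relevant children. Under Protocol 4.1, those who move to the next cohort are the ones who have not improved, while the improved children are directed to the extension. For them the next-cohort cut never operates.

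Part 2 is the only randomized, placebo-controlled safety comparison, and the investigator is blinded (Protocol 5.8), so an offer based on improvement can reach placebo children as well as linaclotide children. Read literally, SAP 10.2.1 assigns an event that starts after a first extension dose, but within 30 days of the last Part 2 dose, to the Part 2 arm. In arms of six, one such event visibly changes a tabulated percentage.

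**Working it through.** The plan states no figure for this point, so there is nothing to reproduce beyond the sample size: 3 × 6 + 12 = 30, which agrees with the SAP. Part 2 has 12 children at 1:1, hence 6 per arm.

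**Timing.** Inputs: 28 days of treatment (Protocol 5.7, Operations Manual 5.2), so last dose is taken as Day 28; Visit 5 on Day 29, +2 days; Visit 6 seven days later, +2 days (Operations Manual 2.1 and 2.2).

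- The TEAE window closes on Day 28 + 30 = Day 58.
- Earliest Visit 6: 29 + 7 = Day 36. Latest, using both visit windows: 31 + 7 + 2 = Day 40.
- Overlap in days = 58 − entry day + 1.
- Entry on Day 36: 58 − 36 + 1 = 23 days (23/30 = 77% of the post-dose tail).
- Entry on Day 40: 58 − 40 + 1 = 19 days (19/30 = 63%).
- Entry on Day 59 or later: 0 days.

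**Weight of one event.** 1/6 = 16.7 percentage points of an arm's TEAE rate.

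**Illustration of likelihood.** Assumptions, none of them settled by the documents: the extension drug is linaclotide; diarrhea risk is 7.6% per 28 days (the rate on linaclotide in LIN-MD-62, ages 6 to 17, Protocol 2.1) with constant hazard; overlap is 23 days; children are independent.

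- Risk per child in the overlap: 1 − (1 − 0.076)^(23/28) = 6.3%.
- Chance of at least one such event among k placebo roll-overs: 1 − (1 − 0.063)^k, giving about 6% (k = 1), 18% (k = 3) and 32% (k = 6).

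**Direction.** Take the LIN-MD-62 rates (7.6% versus 0%) as the true on-treatment difference, and let fL and fP be the fractions rolling over from the linaclotide and placebo arms.

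- Expected linaclotide rate: 7.6 + (0.924 × 6.3) fL = 7.6 + 5.8 fL points. Expected placebo rate: 6.3 fP points.
- Tabulated difference: 7.6 + 5.8 fL − 6.3 fP.
- fL = 4/6, fP = 2/6: 7.6 + 3.9 − 2.1 = 9.4 points, wider than 7.6.
- fL = 2/6, fP = 4/6: 7.6 + 1.9 − 4.2 = 5.3 points, narrower.
- Equal fractions: the difference falls by at most 6.3 − 5.8 = 0.5 points.

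**Hy's law window.** Chemistry is scheduled only at Screening and end of treatment (Protocol Appendix D), and Visit 6 has no laboratory tests (Operations Manual 2.2). Only unscheduled samples could fall in the tail.

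**The case against.** The strongest reply is that the harm depends on a study these documents do not describe. They give no opening date, drug, dose or waiting time for the extension, and do not say which database holds AEs after roll-over. If the extension is not open, or children enter after Day 58, nothing is misattributed. That stands, and it is why the point is that events could be counted, not that they are.

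A reader might infer something stronger: that linaclotide AEs will be booked to placebo and pull the comparison toward no difference. The documents do not support this. The extension drug is not named. Linaclotide-arm children can roll over too, and their late events inflate their own arm; if more of them enter, the difference widens. Nor is entry straight after the last dose supported for completers, because linaclotide is on the list of drugs excluded during the Postintervention Period (Protocol 5.2). This is why the range above starts at Visit 6.

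It can also be said that SAP 10.1 places safety analyses in the 4-week periods, and that the cohort cut separates exposures within one study whereas the extension is another study. The general wording in 10.1 does not override the specific 30-day definition in 10.2.1; the mismatch is a further reason to state the end point. The separate-study argument would help only if the plan said that AEs after roll-over are recorded elsewhere, and it does not.

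Finally, there is no hypothesis test, subject-level safety listings are required (Protocol 7.5), and the dose-selection criteria in Protocol 4.1 and the escalation review in 5.11 do not rest on TEAE tables. All of this stands and limits the severity.

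**Conclusion.** The gap is real. As written, SAP 10.2.1 can attribute an AE that starts on extension treatment to the Part 2 arm or Part 1 cohort just left, and no other section supplies the missing cut. Three conditions must all hold: the extension is active, the child enters within 30 days of last dose, and the event is recorded in this study.

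If entry is around Visit 6, roughly two thirds to three quarters of the post-dose tail would be extension time, and each child misclassified in Part 2 costs 16.7 percentage points in that arm. The direction of distortion is not fixed. The 6%, 18% and 32% figures are illustrations that rest on linaclotide being the extension drug and on a rate from older children.

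Because every analysis is descriptive and late events can be checked in the listings, this is a low-to-moderate issue. It should still be settled before Part 2 is unblinded: with six children per arm, a cut-off chosen afterwards would be post hoc.

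**What to change.** In SAP 10.2.1, for Cohorts 1 to 3 and Part 2 alike, end the TEAE window at the earliest of:

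- first dose in the next cohort, where applicable;
- first dose in the extension study;
- 30 days after last dose.

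Capture the extension first-dose date so that the cut can be programmed, and state in the protocol or SAP which study records AEs after roll-over. For consistency, apply the same cut to the Hy's law summary in SAP 10.3, where the practical effect is minimal.

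The cost is a short SAP edit, one date field and one sentence on AE recording. A few late AEs may move from this study's tables to the extension's. If nobody enters within 30 days, no result changes.
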